4.9 Human Subjects/Ethical Considerations

The Viral Suppression component of the study involves an intervention using FIs to encourage HIV-positive individuals on ART to be adherent to their medications and to maintain HIV VL suppression. This component is public health research. In this component, HIV care sites will be randomized, not individuals, and no de novo individual-level data will be collected. Instead, (de-identified) HIV surveillance data routinely collected by the DOH in the two communities will be analyzed. Because this research involves minimal risk and would be impracticable with informed consent, a waiver of patient informed consent will be requested under 45 CFR 46.116 (c) or (d).

The protocol will be submitted to appropriate IRBs (a central and/or local site IRBs) for ethical review prior to study initiation. Any subsequent modifications to the protocol will be submitted to appropriate IRBs, and, at a minimum, the protocol will be submitted annually for continuing review and approval by these same ethics boards.

No individual data, other than what exists in the surveillance databases, will be collected from study participants in the viral suppression component of this study. To assess the impact of the study on viral suppression in the communities of Washington, D.C. and the Bronx, surveillance data routinely collected by the DOHs will be analyzed. Data from the DOHs will be provided to the study team in a de-identified fashion, as per usual HIV surveillance procedures.

No study-specific laboratory testing will be conducted under this protocol. Therefore, no additional study-related test results will need to be reported to authorities. HIV testing and care data collected during routine clinical care will be reported per local HIV and AIDS reporting requirements.

4.10 Safety Monitoring and Adverse Event Reporting

The study team will not collect or report Adverse Events because there is no biomedical intervention. However, the team will collect and report all social harms that are brought to the attention of study staff members, using a study-specific incident report form. This form will be anonymous and will query common social harms such as altered personal relationships, forced change in housing, and physical violence. The form will also include space for a written narrative to document additional details of any social harm experienced. All research staff will be trained to properly complete the form. As a part

of study training, research staff will also be trained on the provision of referrals to counseling and social service support. Reports of social harms will be reviewed quarterly or more often, if indicated, and reported to the medical officer together with any actions that are taken. Social harms will be summarized and reported to appropriate IRB(s) on an annual basis.

5.0 **PREVENTION FOR POSITIVES**

5.1 Study Objectives for Prevention for Positives

The primary objective of the Prevention for Positives study component is to evaluate the effectiveness of a computer-delivered counseling intervention ("CARE+ Prevention") containing Prevention for Positives messages in addition to SOC compared to SOC alone. Both intervention and control groups will have access to available SOC support and counseling services available to HIV-positive patients at the participating HIV care sites. All participants will have regular assessment of risk behaviors. The objective for this study component will be measured by comparing key self-reported HIV-transmission sexual risk behaviors.

5.2 Design for Prevention for Positives

The Prevention for Positives component of the study is a two-arm, individually randomized, prospective, effectiveness trial to be conducted at 12 HIV care sites (6 within each intervention community). This component will compare CARE+ containing Prevention for Positives messages in addition to SOC with SOC alone. All consenting individuals will be randomly assigned to one of the two arms of the study. In this component of the study, participant informed consent will be obtained for all participants in both of the study arms. Limited medical records data pertaining to HIV disease and individual data will be abstracted and analyzed in this study component.

5.3 Study Population for Prevention for Positives

The Prevention for Positives component of the study will include HIV-positive patients at a select number of participating HIV care sites. These patients will include individuals newly diagnosed with HIV and linked to care, and those established in care. ART use is not required for participation.

5.3.1 Inclusion Criteria

The inclusion criteria for this study component are as follows:

- All individuals who are permitted to consent for HIV care according to New York State or Washington, D.C. law
- Receiving care at the selected HIV care sites in the Bronx or Washington, D.C.
- Have attended the clinic one or more times in the last seven months

- Able to understand either spoken English or Spanish
- Able and willing to provide informed consent

Subjects enrolled into the Prevention for Positives component of the study will participate in the patient survey (see Section 6.0).

5.3.2 Exclusion Criteria

The exclusion criteria for this study component are the following:

- Not seen in the clinic in the last seven months
- History or evidence of altered mentation, inebriation or substance use that would interfere with participation in the study
- Unable or unwilling to provide informed consent
- Participation in another study focusing on HIV prevention for positives

5.4 Study Sites for Prevention for Positives

Participants will be recruited for the Prevention for Positives component of the study from six HIV care sites (three FI sites and three SOC of care sites) in each intervention city.

The three sites among the FI sites and the three sites in the SOC sites in each city will be selected based on the following criteria:

- The highest volume of HIV-positive patients in care
- Site agreement to participate in this component of the study

5.5 Intervention for Prevention for Positives

A modified version of CARE+ for HIV-positives will be used with Audio Computer Assisted Self-Interviewing (ACASI) to measure behavioral risk and to compare a full computer counseling intervention (assesses self-efficacy and motivation, provides tailored feedback on specific risk behaviors, shows skill-building videos, and helps the user make a risk-reduction plan) to a control session consisting only of ACASI ascertainment of risk behavior.

An additional component will be the utilization of the computer-based system described above to measure factors that impact both the acceptability of the interventions utilized in this study and the feasibility of future TNT strategies. Other data, beyond those that can be obtained from routine HIV surveillance data, will be captured including the following:

• HIV testing history and prior experience with linkage/drop out from care (if applicable)

- CD4 cell count (via chart abstraction, not routinely available from HIV surveillance), at study enrollment, and then every 3 months up to and including month 12
- VL (via chart abstraction, not routinely available from HIV surveillance), at study enrollment, and then every 3 months up to and including month 12

CD4 cell counts and HIV RNA levels obtained from month 0 through month 12, will be extracted from participant's medical records to enable individual-level subgroup analyses of adherence and virologic responses among CARE+ participants who are receiving versus not receiving FIs for virologic suppression, as well as other subgroup analyses, such as:

- Behaviors likely to transmit HIV (sexual and parenteral)
- Receipt of and experience with services to promote retention and adherence
- Knowledge of, attitudes towards, and the feasibility of early initiation of ART
- Knowledge of and attitudes towards use of ART for prevention in partners

5.6 Study Procedures for Prevention for Positives

5.6.1 Recruitment Process

Study staff at the HIV care sites will be trained for the Prevention for Positives study procedures and on human subject requirements. Clinic or study staff will systematically approach potential subjects in the waiting room or during consultation and inform them of the study. Brief, anonymous demographic data will be noted for those individuals refusing study participation, to assess comparability to study participants. Persons who are interested in the study will be assessed for eligibility and consented in a private area of the clinic. The study staff will provide information to the participant on the use of the tablet computer and headphones, and assist the participant with the anonymous ID log-in and beginning of the session, after which the staff person will remain nearby only to provide assistance if the participant requests it.

5.6.2 Co-Enrollment Guidelines

Prevention for Positives study participants will be allowed to be enrolled in other studies except those focused on reducing the risk of HIV transmission.

5.6.3 Participant Retention

Once a participant enrolls in the Prevention for Positives component of this study, the research staff will make every effort to retain him/her for 12 months of follow-up in order to minimize possible bias associated with loss to follow-up.

5.6.4 Participant Withdrawal

Participants may voluntarily withdraw from the study for any reason at any time. Participants also may be withdrawn by the study sponsor, site IRBs, government or regulatory authorities, the Investigator of Record (after consultation with the Protocol Chair), or Division of AIDS (DAIDS) Medical Officer.

Participants who elect to withdraw from the study prior to month 12 will be asked to complete one last computer session, however, participants will not be required to do so. Study staff will record the reason(s) for all withdrawals from the study in participants' study records.

5.7 Study Duration for Prevention for Positives

Duration of the Prevention for Positives study component is 12 months.

Patients enrolled in the Prevention for Positives component of the study will complete the CARE+/ACASI tool at baseline (month 0) and every three months thereafter for one year (at months 3, 6, 9, and 12).

5.8 Safety Monitoring and Adverse Event Reporting

Physical and psychological risks of this study are expected to be minimal, as no medical/surgical or pharmacologic procedures are planned. The Prevention for Positives study component addresses sensitive behaviors around sex and social interactions. Questions regarding sex may cause embarrassment or discomfort. Participants will be informed in writing and verbally that they may skip any questions and/or drop out of the study at any time without repercussion. Mental stress identified in the course of the study, such as depression, suicidality and intimate partner violence (IPV) will be followed-up appropriately, with counseling services available through the clinics. Counseling services for any other issues may be requested by participants during their routine appointment at the HIV care site.

Researchers will do everything possible to emphasize and maintain the confidentiality of participants, and safeguards for protecting confidentiality of data will be strictly enforced.

The study team will not collect or report Adverse Events because there is no biomedical intervention. However, the team will collect and report all social harms that are brought to the attention of study staff members, using a study-specific incident report form. This form will be anonymous and will query common social harms such as altered personal relationships, forced change in housing, and physical violence. The form will also include space for a written narrative to document additional details of any social harm experienced. All research staff will be trained to properly complete the form. As a part of study training, research staff will also be trained on the provision of referrals to counseling and social service support. Reports of social harms will be reviewed quarterly or more often, if indicated, and reported to the medical officer together with any actions that are taken. Social harms will be summarized and reported to appropriate IRB(s) on an annual basis.

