3.10 Safety Monitoring and Adverse Event Reporting

The study team will not collect or report Adverse Events because there is no biomedical intervention. However, the team will collect and report all social harms that are brought to the attention of study staff members, using a study-specific incident report form. This form will be anonymous and will query common social harms such as altered personal relationships, forced change in housing, and physical violence. The form will also include space for a written narrative to document additional details of any social harm experienced. All research staff will be trained to properly complete the form. As a part of study training, research staff will also be trained on the provision of referrals to counseling and social service support. Reports of social harms will be reviewed quarterly or more often, if indicated, and reported to the medical officer together with any actions that are taken. Social harms will be summarized and reported to appropriate IRB(s) on an annual basis.

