All study-related information will be stored securely at the study site in areas with access limited to study staff. To maintain participant confidentiality, a coded number will identify all study data and administrative forms. All local databases will be secured with password-protected access systems. Forms, lists, logbooks, appointment books and any other listings that link participant ID numbers to other identifying information will be stored in a separate area with limited access. A participant's study information will not be released without the written permission of the participant, except as necessary to: authorized medical care providers; monitors for the National Institute of Allergy and Infectious Diseases (NIAID) and/or its contractors; representatives of the HPTN Coordinating and Operations Center (CORE) and/or the (Statistics and Data Management Center) SDMC; other government and regulatory authorities; and/or the site IRB.

No study-specific laboratory testing will be conducted under this protocol. Therefore, no additional study-related test results will need to be reported to authorities. HIV care data collected during routine clinical care will be reported per local HIV and AIDS reporting requirements.

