8.3 Study Monitoring

This study will not undergo traditional HPTN monitoring by PPD Research Associates. However, the study will be carefully reviewed by an HPTN SMC and/or external monitoring group on a regular basis. Study elements that will be monitored include data quality, achievement of milestones, and magnitude of utilization of study test and care sites, as well as migration of patients between test and care sites based on their randomization assignments.

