Prevention for Positives. In this component of the study, a subset of patients enrolled at select HIV care sites in the two intervention communities will be randomized either to an intervention arm (receiving computer-delivered intervention for sexual risk reduction plus SOC prevention activities) or to the control arm (receiving only the SOC prevention activities at the care site). Individual-level data will be collected and analyzed. This component is public health research requiring informed consent. Written informed consent will be obtained from participants.

Patient survey. All patients participating in the Prevention for Positives study component will be administered the Patient Survey. Individual-level data will be analyzed. This component is public health research. Written informed consent will be obtained from

participants at the time of consenting for participation in the Prevention for Positives study component.

Provider survey. Providers from participating HIV care sites will be invited to complete a Web-based survey regarding their knowledge, attitudes and practices concerning ART for treatment, frequency of HIV testing, and limited sociodemographic information. The survey will be anonymous, and will collect no identifying information. This component is public health research. Informed consent will be obtained from the provider's completing the survey. Before the survey will display, providers will read the consent and if they agree to participate, will indicate their agreement by clicking a button labeled "I agree." Investigator's Records

Study-specific records will only be located at HIV care sites participating in the Prevention for Positives study component. At these sites, all study source documents (such as informed consent forms and patient ID linkage logs) will be maintained in a locked cabinet or room. Access to these records will be restricted to appropriate study staff members, NIAID, OHRP, government or regulatory authorities, and/or IRB.

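### Social harms, the only harm record in Prevention for Positives, go on an anonymous form that as written cannot be compared by CARE+ arm or counted per person, and this conflicts with the coded-form rule in 5.10

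*Protocol*

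**What the plan says.** Every component's safety text declines to collect adverse events, because there is no biomedical intervention. Expanded HIV Testing (2.9) declines social harms as well. The other four safety sections (3.10, 4.10, 5.8 and 6.10) share one rule: "the team will collect and report all social harms that are brought to the attention of study staff members". Of the incident form they say: "This form will be anonymous and will query common social harms such as altered personal relationships, forced change in housing, and physical violence", and add: "The form will also include space for a written narrative to document additional details of any social harm experienced". No section says that the form carries a study ID, arm or site, or that harms are summarised by arm.

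Section 5.8 does provide for help and review. It says "Mental stress identified in the course of the study, such as depression, suicidality and intimate partner violence (IPV) will be followed-up appropriately", through counseling at the clinics, and "research staff will also be trained on the provision of referrals to counseling and social service support". Reports are looked at no less than quarterly, go to the medical officer with a note of any action, and are summarised for the IRBs each year.

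Two other places bear on the form. For Prevention for Positives, 5.10 states that "a coded number will identify all study data and administrative forms", and 6.9 repeats this for the patient survey. Section 8.5 states: "Study-specific records will only be located at HIV care sites participating in the Prevention for Positives study component". The list in 8.3 reads "Study elements that will be monitored include data quality, achievement of milestones, and magnitude of utilization of study test and care sites", followed by migration of patients between sites. It does not name social harms.

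**The concern.** Randomisation lets a trial say whether an intervention causes more harm than its comparator, but only if each harm can be assigned to an arm. CARE+ asks about and gives feedback on sexual behaviour, and 5.8 itself names intimate partner violence as something the study may bring to light. If the one harm record cannot be split by arm, an excess of partner violence or housing loss under CARE+ would appear only in a combined total. If it cannot be tied to a person, several reports of one event look the same as several events.

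This is not detail left for a later document. The protocol fixes a property of the form, anonymity, and another section of the same protocol fixes the opposite property.

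**Working it through.** The documents give no expected rate, threshold or stopping rule for social harms, so there is no figure to reproduce. The check is a comparison of sections.

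**1. Does site reveal arm?**
- *Prevention for Positives:* no. Individuals are randomised (5.2) by a random number generator in the software (5.9.3). Planned enrolment is 1,320 / 12 = 110 per site, with both arms at each. The 12 sites are six FI and six SOC care sites (5.4), so site gives the incentive arm but not the CARE+ arm.
- *Linkage-to-Care and Viral Suppression:* yes, if the randomised site is recorded. That is the test site in the first (3.4) and the care site in the second (4.4).

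**2. What can be learned from *k* reports in Prevention for Positives?**

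| Form carries | Split of *k* reports by CARE+ arm | Number of people affected | Link back after filing |
|---|---|---|---|
| Neither ID nor arm | anything from 0 : *k* to *k* : 0 | anything from 1 to *k* | no |
| Arm only | known | unknown | no |
| Coded study ID | known | known | yes, through the ID log |

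The denominators are known (660 planned per arm). What is missing is the numerator by arm. The narrative space might sometimes reveal the arm or a repeat report, but nothing ensures that it does.

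**3. Is the form coded or unlinked?** By 5.8 and 6.10 it is anonymous. By 5.10 and 6.9 every study form carries a coded number. The protocol uses the word anonymous in two senses. In 5.6.1 (demographics of people who refuse) and in 6.9 (the provider survey) it means unlinked. In 5.6.1 (tablet log-in), 6.5 and 6.8 it describes a unique study ID, and in 6.5 randomisation follows log-in with that ID. A site could follow either sense.

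**4. Is capture active anywhere?** Neither the data list in 5.5 nor the schedule in Appendix I names a social-harm question, although participants have sessions at months 0, 3, 6, 9 and 12. The computer questionnaire is not in the protocol, so it cannot be said that no session asks. The only stated rule is passive.

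**5. Where can the form be kept?** Sections 3.10 and 4.10 require a study-specific incident form in the two incentive trials. Section 8.5 places study-specific records only at Prevention for Positives sites. Sections 3.8.4 and 4.8.4 also have participating sites keep tracking logs, so 8.5 cannot be taken literally as it stands.

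**The case against.** The strongest reply is that this is loose wording. The form's fields are not shown, and data collection procedures are left to the procedures manual (8.2). An arm or site field is compatible with anonymity, and the protocol elsewhere calls a unique study ID anonymous. The coded-number rule in 5.10 may therefore already govern the form. Risks are described as minimal, so whether to ask about harms actively is a matter of judgement. Much of this stands: the form may turn out to be coded. But a manual cannot settle the matter while the protocol states both rules, and the unlinked reading is the plain sense of 5.8.

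Four stronger readings are tempting, and the documents do not support them.

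- *That a harm cannot be followed up.* Section 5.8 provides clinic follow-up of distress and partner violence, referral, and review with action noted. Anonymity removes only the later link from a filed report to a person.
- *That 8.3 is the only regular review.* Section 5.8 has its own quarterly review and annual IRB summary. The list in 8.3 is introduced as inclusive, so omission there is not exclusion.
- *That reporting in the incentive trials must differ by arm.* The 40 selected care sites include the SOC sites of Viral Suppression, and 3.4 has the care sites redeem coupons. SOC care sites therefore also handle the study's gift cards. Arm-dependent reporting is plausible only at SOC test sites.
- *That a coded form would let an absence of reports bound the risk.* Under passive capture it would not. Counts by arm would still be minimum counts.

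**Conclusion.** The point holds for Prevention for Positives. As written, the only harm record for 1,320 planned participants cannot be compared between the two arms of 660, counted once per person, or linked to a participant after filing. The wording also contradicts 5.10 and 6.9. The conclusion rests on reading anonymous as carrying no identifier, and on no arm field having been added elsewhere. If the form does carry the coded ID, what remains is a contradiction to be corrected in the text.

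In the two site-randomised components the gap is smaller. Arm is recoverable once the form records the randomised site, which the protocol does not state. No number of missed harms can be given, because the documents offer no rate. The change is worth making: it alters a stated rule, costs little, and permits a comparison that the design otherwise supports.

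**What to change.** 1. In 5.8, and in 6.10 for patients, replace the anonymous form with one identified by the coded study ID and no name. This brings both into line with 5.10 and 6.9. Reports arising from the provider survey can stay unidentified.
2. In 3.10 and 4.10, record component and randomised site, with no personal identifier. Arm then follows from site, and the commitment to collect no new individual-level data is kept.
3. Summarise social harms by arm in the existing quarterly review, and name them among the items in 8.3.
4. Reconcile 8.5 with the incident form required in 3.10 and 4.10, stating where that form is held.

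Cost: one or two fields on the form and one table per review. The form becomes coded rather than anonymous, under the storage and access protections already set out in 5.10.

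Optional: a short standard social-harm item at months 3, 6, 9 and 12 in both arms. With the attrition assumed in 5.9.2, it would be asked at about 1,320 × 0.90 × 3.75 = 4,455 sessions. It would inform the CARE+ comparison only, because consenting participants at 12 selected care sites give no denominator for the incentive trials. Sessions would be slightly longer, and positive answers would have to be routed to the clinic counseling that 5.8 already describes.
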